10.5 Reporting Procedures For Adverse Events

10.5.1 General Reporting Requirements - Non-Serious Adverse Events

The Investigator (or designee) will record **all** AEs (both serious and non-serious and regardless of relationship) in the source documents. AEs will be reported on the eCRF (except those in Section 10.2 as described) from the time of treatment (induction of anesthesia) through Visit 11. Only the AEs listed to be collected (Section 10.5.2) in the annual visits (2–5-year visits) will be reported on the eCRF. Prior to induction of anesthesia, any events will be considered patient medical history. Standard medical terminology should be used when recording AEs. The information as described in 10.3 and 10.4 should be recorded for each AE. The following criteria must also be adhered to by the Investigator:

- Use separate Adverse Event Form to document each series of events.
- The Adverse Event Form must be electronically signed by the Investigator or Co-Investigator (if applicable).
- It is the responsibility of the Investigator to inform their IRB of SAEs as required by their IRB/EC procedures and in conformance with FDA requirements.

Note: It is the responsibility of the Investigator to inform their IRB of non-serious adverse events, as required by their IRB procedures and in conformance with FDA requirements.

10.5.2 Reporting Requirements – Serious and Unanticipated Adverse Events

Serious and any unanticipated adverse events up to Visit 11 (12 month post endocardial procedure) must be reported by the Investigator (or designee) by submitting the Adverse Event Electronic Case Report Form to the Sponsor, within 10 days of becoming aware of the adverse event. An event determined by the Investigator to be life threatening or to have led to death should be reported within 24 hours.

From subject treatment (induction of anesthesia) through Visit 11 all SAEs are reported except those listed in Section 10.2. After Visit 11 through Visit 15 or Subject Exit, SAEs are reported on the eCRF if they are any of the following: death (regardless of cause), stroke, transient ischemic attack (TIA), myocardial infarction (MI), pulmonary or systemic embolism, permanent pacemaker implantation, device related, procedure related, or UADE.

In the event of system outages or technical difficulties, serious and any unanticipated adverse events may be submitted via e-mail to [contact]. Upon availability of the system or resolution of the technical difficulties, the event will be recorded in the Adverse Event eCRF.

The Investigator (or designee) shall send a written report including a narrative description of the

serious and/or unanticipated adverse event to AtriCure or their designee within three (3) working days of the initial report. The Investigator should follow all unresolved serious adverse events until the events are resolved, or the subject has exited the study, or the adverse event is otherwise explained.

AtriCure, Inc., or their designee, in cooperation with the Investigator, will assess all serious adverse events considered device-related for potential reportability to the FDA as an Unanticipated Adverse Device Effect (UADE) in accordance with 21 CFR Part 812.46(b). If a UADE determination is made, the Investigator and Sponsor will comply with UADE reporting requirements per 21 CFR Part 812.150. The Sponsor shall report the results of such evaluation to FDA and to all reviewing IRBs/ECs and participating Investigators within ten (10) working days after the Sponsor first receives notice of the UADE. Thereafter the Sponsor shall submit such additional reports concerning the effect as FDA requests. Similarly, the Investigator shall submit to their reviewing IRB a report of any UADE as soon as possible, but in no event later than ten (10) working days (or per local IRB requirements) after the Investigator first learns of the effect. The Investigator (or designee) shall provide documentation of the UADE report/notification sent to their IRB to AtriCure (or designee).

Note: It is also the responsibility of the Investigator to inform their IRB of other SAEs (i.e., non-UADEs) as required by their IRB/EC procedures and in conformance with FDA requirements.

- If the subject reports any adverse events that are potentially serious during the follow-up evaluation period, the subject should return to the investigator's facility for further evaluation of the event.

Note: If the subject exhibits symptoms suggestive of pulmonary vein stenosis, CT/MR imaging should be performed.

10.5.3 Subject Death and Atrio-esophageal Fistula

The investigator (or designee) must report any reported death (determined to be device or procedure related) and/or atrio-esophageal fistula during conduct of this study to the sponsor, within 24 hours of learning of the adverse event by submitting the adverse event eCRF. The investigator must electronically sign the electronic adverse event form. A copy of medical records, supporting documents (CT scans, ECGs, consult records), death records, death certificates and an autopsy report (if performed) are required to be sent to the AtriCure or designee within 10 days following the death.

Any reported death (determined to be device or procedure related) and atrio-esophageal fistula during the conduct of this study, will be reported to the FDA within 10 days.

In addition, subject deaths (determined to be device or procedure related and atrio-esophageal fistula must be reported to the IRB/EC in accordance with IRB/EC requirements.

In the event of a reported atrio-esophageal fistula study enrollment will be put on pause (see Study Stopping Rules Post-Surgical Ablation).

10.5.4 Study Stopping Rules Post-Surgical Ablation

In the event that a new esophageal injury is adjudicated by the core lab as a thermal injury with perforation related to the study index Epicardial Procedure [e.g., atrio-esophageal fistula or pericardioesophageal fistula or other esophageal perforation but without fistulous connection to the left atrium or pericardial sac] is confirmed between Visit 2 until the start of Visit 7, the following will occur:

- AtriCure will notify the FDA within 10 working days of AtriCure awareness.
- AtriCure will also notify the Site Investigators within 10 working days of AtriCure awareness and immediately pause further Epicardial Procedures and consent of new subjects.

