7.17 AEF Unscheduled Visit

AEF Unscheduled visit in the event of suspected AEF after Visit 3 or Visit 5. If AEF is suspected, endoscopy and/or TEE probes should be avoided.

- Assessment of AEF symptoms

Note: Hospital Standard of Care will be followed to assess, diagnose and treatment when AEF is suspected. A computed tomography scan is the typical tool used to diagnose AEF. Since a CT scan may be conducted early in the course of AEF diagnosis, a repeat CT image should be considered if the initial CT scan is normal, but symptoms and findings indicative of AEF do not resolve.

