11.3 Core Laboratories

ECG Core Laboratory

An independent ECG core laboratory will be utilized for assessment of the following data collected on subjects. All data submitted to the core laboratory will be reviewed and the core laboratory will interpret the reading.

- Visit 10 and Visit 11: ECG collected at follow-up study visits
- Visit 10 and Visit 11: Continuous ECG monitoring recordings (Holter or ZioTM Patch)
- Visit 10 thru Visit 11: Symptom driven monitoring

All ECG monitoring shall be performed in accordance with the core laboratory's recommended protocol which is provided to the sites in the Study Reference Manual.

Imaging Core Laboratory

Left Atrial Appendage: An independent core laboratory will be utilized for assessment of the complete exclusion of the LAA defined by lack of fluid communication (<3 mm residual communication with LAA and < 10mm residual pocket) between the LA and LAA.

Images to be sent by the site include:

- Visit 5: (TEE) Endocardial Procedure Visit
- Visit 11: (CT/CTA/MRI) 12-month post Endocardial Procedure Visit.

Pulmonary Veins: If a subject exhibits symptoms suggestive of pulmonary vein stenosis, the baseline and subsequent CT/MR imaging will be submitted by the site to an independent imaging core laboratory for analysis.

- Images sent to core lab (as applicable) for Visit 4, Visit 10, Visit 11

Consistent with the recommendation from the 2012 HRS/EHRA/ECAS Expert Consensus Statement in Surgical and Catheter Ablation of AF, PV stenosis is categorized as mild < 50%, moderate 50-70% and severe ≥ 70% reduction in the diameter of a PV or PV branch.

Esophagoscopy Core Laboratory

Esophagoscopy (EGD): An independent core laboratory will be utilized for adjudication of any esophageal injuries discovered on the post epicardial procedure EGD. All data submitted to the core laboratory will be reviewed and the core laboratory will provide adjudication. An esophagoscopy at Visit 2 will be performed as a baseline assessment. An esophagoscopy at Visit 3 is to be performed 24 to 72 hours post Procedure. If the esophagoscopy at Visit 3 reveals a new acute esophageal injury, subject reports, images, data and relevant documents will be submitted to a core lab.

REFERENCE LIST

¹

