5.6.4.8 Secondary Safety Endpoint #8

The statistical analysis of secondary safety endpoint #8 will consist of an estimate of the proportion of patients with any esophageal injury through 30-days post epicardial procedure. This will include all esophageal injuries that meets all of the following criteria: identified post epicardial ablation, adjudicated by core lab to be a thermal injury with perforation, and related to an AtriCure ablation device. The safety population will be used for this analysis. Missing observations will be excluded.

The proportion will be calculated with subjects as the experimental unit. The numerator of the proportion will be the number of subjects with an esophageal injury and the denominator will be the total number of subjects without a missing observation. The endpoint will be presented with the numerator and denominator, the proportion and its 95% two-sided exact binomial confidence interval.

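### Protocol 10.5.3 and 10.5.4 give different esophageal-injury pause rules, and the core lab that 10.5.4 and secondary safety endpoint #8 rely on has no stated route for CT-diagnosed cases

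*Protocol*

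**What the plan says.** Protocol 10.5.3 requires any atrio-esophageal fistula (AEF) to be reported to the sponsor within 24 hours of the site learning of it. It continues: "In the event of a reported atrio-esophageal fistula study enrollment will be put on pause", and refers to the stopping rules in 10.5.4.

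Protocol 10.5.4 opens: "In the event that a new esophageal injury is adjudicated by the core lab as a thermal injury with perforation". The injury must also be "related to the study index Epicardial Procedure", and the rule applies if it "is confirmed between Visit 2 until the start of Visit 7". AEF, pericardioesophageal fistula and perforation without a fistula are given as examples. The sponsor must then "notify the Site Investigators within 10 working days of AtriCure awareness and immediately pause further Epicardial Procedures" and stop consenting new subjects.

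On the core lab, Protocol 11.3 says: "An independent core laboratory will be utilized for adjudication of any esophageal injuries discovered on the post epicardial procedure EGD". Material is submitted when the Visit 3 esophagoscopy (EGD), done at 24 to 72 hours, shows a new acute injury. Schedule footnote 25 and the Visit 3 text in 7.3 place submission in the same setting.

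For later suspicion, Protocol 7.17 says: "If AEF is suspected, endoscopy and/or TEE probes should be avoided", and names CT as the usual diagnostic tool. The AEF definition in Appendix 5 also advises against esophagoscopy.

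SAP 5.6.4.8 counts, through 30 days after the epicardial procedure, injuries "adjudicated by core lab to be a thermal injury with perforation, and related to an AtriCure ablation device".

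**The concern.** The only explicit pause rule in the protocol concerns a potentially fatal complication, and it is written in two adjacent sections that do not match. At up to 35 sites, careful readers could disagree on whether scheduled epicardial procedures go ahead after a late fistula is reported.

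The 10.5.4 trigger and endpoint #8 also both depend on adjudication by a core lab. The protocol looks for fistulas after Visit 3, through the day-18 call, the symptom check at Visit 4 and the AEF unscheduled visit. Its own work-up for these cases steers away from the examination that feeds the core lab. A perforation could then be diagnosed and known to the sponsor, yet not formally satisfy the stopping rule or enter the endpoint count.

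**Working it through.** **1. The two pause rules side by side**

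| | 10.5.3 | 10.5.4 |
|---|---|---|
| Trigger | AEF reported | Thermal perforation adjudicated by the core lab |
| Injuries covered | AEF only | AEF, pericardioesophageal fistula, perforation without fistula |
| Attribution | None stated | Index epicardial procedure |
| Window | None stated | Visit 2 to start of Visit 7 |
| What is paused | Study enrollment | Epicardial procedures and new consents |

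The last row matters because Protocol 4.2.2 defines enrollment as signing consent, and 7.2 allows surgery up to 45 days after consent. Read literally, an enrollment pause does not stop surgery in subjects who have already consented; only 10.5.4 does. The cross-reference from 10.5.3 to 10.5.4 does not say whether a report alone brings the wider pause into force.

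**2. The route to the core lab**

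- Protocol 11.3, footnote 25 and 7.3 start from the post-epicardial EGD.
- Protocol 7.17 and Appendix 5 direct suspected AEF away from endoscopy and name CT. No core-lab step is stated for that CT.
- The imaging core lab in 11.3 covers the left atrial appendage and the pulmonary veins only.
- Under 10.5.3, CT scans and other records go to the sponsor or its designee. The 10-day limit for sending them runs from a death, so a non-fatal fistula has no stated deadline.

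**3. Length of the 10.5.4 window against the EGD**

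Inputs: endocardial procedure (Visit 5) on day 91 to 121 (7.7); Visit 7 at 7 days, plus at most 1, after it (7.10); EGD at 24 to 72 hours, that is days 1 to 3 (7.3).

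- Earliest end on schedule: 91 + 7 = day 98. EGD share at most 3/98 = 3.1%.
- Latest end on schedule: 121 + 8 = day 129. EGD share at most 3/129 = 2.3%.
- Catheter stage brought forward under 7.4, allowed only after Visit 4 (day 30 at the earliest). Assuming day 31: 31 + 7 = day 38. EGD share at most 3/38 = 7.9%, leaving about 92% of the window.
- Visit 7 never occurs (withdrawal before the catheter stage, or conversion to sternotomy or thoracotomy; 4.4 and 7.2): no defined end.

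**4. Endpoint #8**

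The endpoint period is 30 days and the EGD falls in days 1 to 3. Days 4 to 30, that is 27 of 30 days, have no expressly stated route for a perforation first found by CT.

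**The case against.** Several points weigh against a stronger reading.

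- A reader might infer that a late CT-diagnosed fistula would not pause the study at all. The documents do not support this: under 10.5.3 the report alone pauses enrollment. Section 10.5.4 does not say that it is the only trigger, so the two sections could be meant as two sufficient triggers. That stands, and it narrows the problem to surgery in already-consented subjects and to late perforations other than AEF.
- A reader might take the shares above as the proportion of events missed. They are shares of calendar time, and nothing in the documents says when perforations would occur.
- It would be wrong to say that no EGD exists. Baseline and 24-to-72-hour EGDs are required. What may be lacking is an endoscopic record of the late event itself.
- One sentence in 7.3 on detected esophageal injuries could be read as a wider referral duty, and 7.3 recommends repeat imaging within 14 days once an injury is seen. Both 10.5.4 and endpoint #8 also presume that the core lab adjudicates later cases. This makes the remit wider than 11.3 states, but still gives no route for a CT finding. The Safety Monitoring Plan (10.6.1) may say more; it is not among the documents.
- The 10 working days is a maximum for notifying sites, set beside a separate duty to pause at once. It is not a stated delay. The protocol only leaves unclear how sites learn of an immediate pause.
- Other safeguards remain: the DSMB's confidential stopping rules (11.2), CEC adjudication (11.1), and AEF in the primary safety composite through 12 months (Protocol 3.2, SAP 2.1.2; the synopsis says the 1-month visit). None of these meets the core-lab condition in 10.5.4 or in endpoint #8.

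**Conclusion.** The concern holds as a contradiction between 10.5.3 and 10.5.4 plus an under-described referral route. It should be fixed, but it does not leave subjects without other protection and does not touch the primary analyses.

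Two cases are exposed. After a late AEF report, enrollment stops but the status of surgery in already-consented subjects is contradictory. A late pericardioesophageal fistula, or perforation without fistula, depends on 10.5.4 alone and hence on an adjudication with no stated route if it is found by CT.

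The number of cases affected cannot be derived from the documents. Endpoint #8 is exploratory and untested, so a missed case would affect the reported safety profile, not a success criterion. The conclusion assumes the 7.3 sentence is confined to its Visit 3 setting and that no document outside this set supplies the missing route.

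**What to change.** 1. Reconcile 10.5.3 and 10.5.4 into one consistent statement of trigger, attribution, window (including when Visit 7 never occurs) and what is paused. Clarify how the notification limit fits with an immediate pause. The content is for the sponsor and its safety bodies to choose.
2. Amend 11.3, 7.3 and footnote 25 so that any esophageal perforation or fistula, however found, is referred for core-lab adjudication from existing records (CT, operative, autopsy). This should cover the endpoint #8 period, and also the 10.5.4 window if adjudication remains part of the reconciled rule. State a submission deadline for non-fatal cases.
3. Count in endpoint #8 every referred case that meets its definition.

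The cost is protocol wording, a charter update confirming that the core lab can review non-endoscopic records, and a few more cases to adjudicate. No subject undergoes an additional procedure.

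### Sections 10.5.2, 10.5.3 and 10.5.4 do not fit together: the esophageal-perforation pause is immediate, but its site notice and injury-reporting time limits are not aligned with it

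*Protocol*

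**What the plan says.** Protocol Section 10.5.4 applies when "a new esophageal injury is adjudicated by the core lab as a thermal injury with perforation related to the study index Epicardial Procedure". Its examples are "atrio-esophageal fistula or pericardioesophageal fistula or other esophageal perforation but without fistulous connection" to the left atrium or pericardial sac. Two sponsor actions follow. The first concerns FDA: "AtriCure will notify the FDA within 10 working days of AtriCure awareness". The second is to "notify the Site Investigators within 10 working days of AtriCure awareness and immediately pause further Epicardial Procedures", and with them the consenting of new subjects.

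Two other sections govern how the sponsor learns of such an injury.

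- Section 10.5.3 obliges the investigator to report a device- or procedure-related death "and/or atrio-esophageal fistula during conduct of this study to the sponsor, within 24 hours of learning of the adverse event". It adds that a reported atrio-esophageal fistula puts enrollment on pause, with a cross-reference to the stopping rule, and that the fistula "will be reported to the FDA within 10 days".
- Section 10.5.2 gives the general rule for serious and unanticipated events: report "within 10 days of becoming aware of the adverse event". Events that the investigator judges life threatening, or that led to death, should be reported within 24 hours.

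Section 7.3 (Visit 3) has esophageal injuries found on the 24-72 hour esophagoscopy sent to a core lab. Neither that section, Section 10.5.4 nor Section 11.3 sets a time limit for submission or adjudication.

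**The concern.** The rule exists to protect the next subject from an injury grave enough to halt surgery. It can do so only if the sponsor hears of the injury quickly and the operating sites hear of the pause quickly. The protocol sets time limits for both messages, and neither limit matches the immediacy of the pause.

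Up to 35 sites operate and take consent, and a pause they have not heard of stops nothing. On the reporting side, an injury on the trigger list may reach the sponsor in one day or in ten. Which it is depends on whether the injury is an atrio-esophageal fistula and, if not, on how the investigator classifies it.

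**Working it through.** There is no plan figure to reproduce. The check sets the stated limits side by side and adds them.

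**Inputs.** Site to sponsor: 24 hours (10.5.3, or the life-threatening/fatal route in 10.5.2) or 10 days (10.5.2 default). Core-lab adjudication: not stated; call it A. Sponsor to sites: 10 working days from sponsor awareness (10.5.4). Pause: immediate (10.5.4).

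**Step 1: convert the notice limit.** Ten working days from any weekday is 14 calendar days. From a Saturday it is 13 and from a Sunday 12. Holidays lengthen it.

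**Step 2: pause against notice.** If sites stop only when notified, the longest lag the notice limit allows is about 14 calendar days from sponsor awareness. If the sponsor tells sites at once, as an immediate pause implies, the lag is about 0. The sentence contains both timings and does not say how the pause reaches sites before the notice.

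**Step 3: trigger list against reporting limits.**

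| Injury in 10.5.4 | Named in 10.5.3 (24 h, mandatory) | Limit otherwise (10.5.2) |
|---|---|---|
| Atrio-esophageal fistula | Yes | Not needed |
| Pericardioesophageal fistula | No | 10 days; 24 h if judged life threatening or fatal |
| Other perforation without fistula | No | 10 days; 24 h if judged life threatening or fatal |

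One of the three has an unconditional 24-hour limit.

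**Step 4: time from site awareness to the end of the notice limit.** This takes sponsor awareness to mean awareness of the adjudicated trigger.

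- 24-hour route: 1 + A + 14 = 15 + A days.
- Default route: 10 + A + 14 = 24 + A days.

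With A assumed to be 0, 7 or 14 days, for illustration only, the totals are 15, 22 or 29 days on the 24-hour route and 24, 31 or 38 days on the default route. The two routes differ by 10 − 1 = 9 days.

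These totals start when the site learns of the injury. The trigger is the core lab's adjudication, and the SAE report normally comes before it. The part that follows sponsor awareness of the trigger is only the 14 days of Step 1. If sponsor awareness instead means receipt of the site's report, A falls inside the 10 working days and is not added.

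**Step 5: FDA notice for an atrio-esophageal fistula.** The limits are 10 days (10.5.3) and 10 working days, about 14 calendar days (10.5.4). If the former means calendar days, the difference is 14 − 10 = 4 days.

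**The case against.** The strongest reply is that Section 10.5.4 sets two separate duties. The pause has its own timing, and ten working days is only an outer limit for notice. Section 10.5.2 gives the same limit for reporting unanticipated adverse device effects to FDA, IRBs and investigators, so it may be meant as a formal-report deadline. A sponsor that let surgery run on until day 10 would breach the immediate pause. This stands as far as it goes: nothing in the text permits procedures to continue. What it leaves open is how sites learn of the pause before the notice, since no earlier communication is stated.

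A reader might infer that surgery can go on for weeks after a trigger, or for 24 days after it. The documents support neither reading. The pause is ordered at once, and the 10-day reporting leg normally precedes the trigger. A reader might also infer that no 24-hour route exists for the other two injuries. Section 10.5.2 provides one, but it depends on the investigator's judgement or a fatal outcome.

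Other provisions may narrow the gap. Section 10.5.3 pauses enrollment on a reported atrio-esophageal fistula without waiting for adjudication, though that covers one injury and speaks of enrollment. Esophagoscopy findings also go to the core lab apart from the SAE form, with no deadline. The Safety Monitoring Plan (10.6.1) and the DSMB charter (11.2) may contain operational steps. Neither is among the documents, so this cannot be confirmed or excluded.

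On FDA notice, the two limits attach to different stages, a reported fistula and an adjudicated injury. Meeting the shorter satisfies both, and neither affects when sites stop. That part is minor.

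**Conclusion.** The inconsistency is real and should be corrected. It has two substantive parts and one minor part.

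1. The notice limit can be met about 14 calendar days after sponsor awareness, while the pause it announces is immediate and has no other stated route to the sites. The lag arises only if the pause takes effect on notification.
2. Two of the three named trigger injuries lack an unconditional 24-hour report. A site can comply by reporting a non-fistulous perforation on day 10 if it was neither judged life threatening nor fatal. This lengthens the time from site awareness, to which an unstated core-lab time is added.
3. FDA notice for the same fistula is given in two different units.

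No count of subjects operated on in the interval is offered as support. It would need an accrual period, which the documents do not give. The point rests on the wording of the three sections and on what compliance with each limit would allow.

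**What to change.** Reconcile Sections 10.5.2, 10.5.3 and 10.5.4 so that:

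- the site-to-sponsor reporting time is consistent across all injuries on the Section 10.5.4 trigger list;
- the site-notification time agrees with the immediate pause;
- the FDA notice time for the same event is stated once.

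The sponsor sets the values; no reporting time or clinical rule is proposed here. If the Safety Monitoring Plan or the DSMB charter already contains such steps, a cross-reference would serve for those parts.

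The cost is about three sentences in a protocol amendment, with the usual IRB/EC review, and a notice to sites. No new data or procedures are needed.
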